A blood sample (approx. 10 ml) will be collected at the weeks 8 and 13 for measurement of biological markers of alcohol use (PEth and GGT). GGT measurements will be performed by a Madigan laboratory and results will be placed in the participant's AHLTA record. GGT results will be reported to the participant as clinically indicated and the participant will be referred for medical follow-up, if clinically indicated. PEth samples will be shipped for analysis; however, results will not be available in real time. These results will not be reported to the study participant or to any person not involved in the research.

Study drug adherence will be tracked by pill counts at each study visit.

The blind will be broken at the end of the week 13 visit. Procedures for breaking the blind are described in detail below.

Week 19—6-week follow-up: On week 19 (6 weeks after completion of the week 13 visit), participants will be asked to return for a follow-up visit. At this visit, all outcome assessments (CAPS, alcohol use calendar, PACS, SIP, PSQI, PCL-M, and PHQ-9) will be administered. A blood sample (approx. 10 ml) will be collected for PEth and GGT measurement. Participants will receive a certificate of appreciation at this visit or at the early discontinuation visit as appropriate.

Study personnel will have access to participants' medical records during the period of study participation and for 30 days after study completion or early discontinuation. Records will be reviewed to monitor for changes in health, adverse events, any laboratory results, and completion status of the treatment program. Laboratory results may include urine toxicology screens performed as part of the participant's treatment. Other than the labs listed as being done at screening visit and the GGT that will be obtained at baseline and weeks 8, 13, and 19, no clinical labs will be done as part of the study.

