11.0 Statistical/Data Analysis Plan

11.1 Statistical Considerations:

List the statistical methods to be used to address the primary and secondary objectives, specific aims, and/or research hypotheses. Explain how missing data and outliers will be handled in the analysis. The analysis plan should be consistent with the study objectives. Include any sub-group analyses (e.g., gender or age group). Specify statistical methods and variables for each analysis. Describe how confounding variables will be controlled in the data analysis

Primary Outcome Measures: Analysis of the primary outcomes will follow the ITT principal. For each of the two outcomes, a linear regression model with covariates that include treatment group, the stratifying variables, and baseline value of the outcome will be used to compare the prazosin and placebo groups at 13 weeks. In addition, we will conduct a repeated measures analysis using data from the two points of follow-up (8 and 13 weeks). The repeated measure analysis will be conducted by comparing response profiles between prazosin and placebo groups. An initial comparison will be conducted using the general estimating equations (GEE) method of Liang and Zeger,⁹¹ which allows all observed data points for each participant. Secondarily, an analysis of covariance (ANCOVA) rate of change analysis will be done as a confirmatory or sensitivity analysis. Stratifying variables will be included as covariates in each model since they are factors in the stratification. It is anticipated that a retrieved dropout strategy will

result in a limited number of missing observations. For the GEE analysis no imputation strategy is required. For the ANCOVA analysis the missing data patterns will be evaluated between the treatment groups. If the patterns are similar and the magnitude of missing data is small, a conventional last observation carried forward (LOCF) imputation will be performed. If the amount of missing data is substantial and/or the patterns of missingness disparate, as an alternative to the traditional ANCOVA, the summary statistic method of Dawson⁹² will be employed. This method has been shown to be robust to non-ignorable missingness. The approach summarizes the response profile using a least square slope, and stratifies on the missing data pattern. We will also run analyses to assess the interactions between treatment group and gender.

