13.0 Recruitment and Consent

13.1 Please describe the recruitment process, including how subjects will be identified and selected for the study.

Participants will be recruited from SMs DBH treatment programs including Substance Use Disorders Clinical Care (SUDCC). No participant will be excluded based upon race, ethnicity, or gender. Racial, ethnic, and gender distribution of the participants is expected to mirror the demographics of SMs undergoing treatment in the DBH. SMs enter these programs from multiple referral sources: self-referral, command direction, medical referral, etc.

The number of SMs referred to the standard outpatient alcohol treatment programs is approximately 150 per month for pure AUD without concomitant use of other drugs of abuse (e.g., marijuana, cocaine, methamphetamine, DMA, and opiates). The average age is 24 with a range of 21-55 years. The racial composition is 70% Caucasian, 21% African American, 6% Asian American/Pacific Islander, 3% Native American. The Hispanic ethnicity of the referred population is 10% Hispanic, 90% non-Hispanic. Gender composition is 10% women, 90% men.

We will not enroll any members of “special vulnerable populations.” Although SMs may have command requirements to complete the clinical outpatient JBLM assignment to the SUDCC programs, command pressure to participate in this research study will be strictly avoided. If a participant becomes incarcerated for longer than one day after the Baseline, the participant will be discontinued from the study. Participants who have been discontinued from the study during the screening phase (e.g., do not currently meet inclusion/exclusion criteria) may be re-screened at a later date. Those discontinued following randomization will not be eligible for re-enrollment.

13.2 Compensation for Participation:

Under 24 USC 30, payment to Federal Employees and Active Duty military personnel for participation in research while on duty is limited to blood donation and may not exceed \$50 per blood draw. They may not receive any other payment or non-monetary compensation for participation in a research study unless they are off duty or on leave during the time they are participating in the protocol.

Participants will be compensated with a \$50 gift card per blood draw (up to five blood draws total, up to \$250 value). They will receive a \$50 gift card after each visit at which a blood draw is performed (screen, baseline, weeks 8, 13 and 19).

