Study Discontinuation or Termination: If the participant is not able to tolerate a minimum dose of 3 mg /day of placebo/prazosin, he or she will undergo early termination and all week 13 assessments will be performed; the participant will be referred to his/her primary mental health care provider for further management. Reasons for early discontinuation or withdrawal will be recorded.

Participants may be discontinued prematurely from study treatment to manage deterioration of clinical status. Specifically, dangerousness toward self or others or emergence of acute psychiatric symptoms necessitating hospitalization will result in discontinuation from the study. If at any time during the study, psychiatric symptoms become markedly increased resulting in severe participant distress or presenting immediate danger to self or others, the participant will be discontinued from the study. In case of need for increased level of care or emergent care, study personnel will provide a warm hand-off to DBH personnel. DBH personnel will assume responsibility for arranging appropriate care.

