Women of childbearing potential must have a negative urine pregnancy test at screen and within one week of starting study drug. Female participants must agree to abstain from sexual relations that could result in pregnancy or use an effective method of birth control acceptable to both participant and the study clinician during the study in order to be eligible. Women who are nursing will not be eligible for study participation. Any woman who becomes pregnant during the course of the study will be discontinued from the study but will continue with customary AUD treatment or treatment with her DBH provider.

Risks of medication side effects will be minimized by starting at a low dose and titrating up to the maximum dose over a period of weeks, by maintaining frequent contact with study participants, and by performing safety assessments on a regular schedule. As a further precaution, male participants will be advised to sit on the toilet for urination during the first week of dose titration.

Vital signs, including orthostatic BP and HR, will be performed at all in-person study visits. Systolic and diastolic BP and HR will be obtained following at least 10 minutes of seated/supine posture and then repeated following 2 minutes of standing. Occurrence of lightheadedness, dizziness on standing, palpitations, drowsiness, headache, nausea, nasal congestion, peripheral edema, and other adverse effects will be rated by a study clinician. For vital signs parameters, unacceptable side effects will include seated/supine hypotension (seated/supine systolic BP < 90) and clinically meaningful orthostatic hypotension (≥ 20 mmHg drop in systolic BP accompanied by lightheadedness or syncope).

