Safety procedures specific to the war zone trauma population: Participants will be discontinued from the study to manage marked deterioration of clinical status or if the study clinician determines the participant is not stable enough to continue participation. For example, psychiatric symptoms become markedly increased resulting in severe participant distress, dangerousness toward self or others or emergence of acute psychiatric symptoms necessitating hospitalization. Study termination will be followed by a warm hand-off to DBH personnel. DBH personnel will assume responsibility for arranging appropriate care. A study clinician will be on call at all times to receive telephone calls from participants regarding any adverse events; participants will be provided with a 24-hour emergency contact number.

Participants are asked about suicidal ideation at each visit. If endorsed, participants will be assessed as to their level of risk and the level of care required to keep themselves or others from harm. If a participant requires inpatient treatment in order to prevent harm or is found to have symptoms of disorganized thought processes secondary to psychosis, DBH personnel will be notified immediately to assist with appropriate triage and referral.

Protection against risk of loss of confidentiality: Confidentiality is strict. All case report forms (CRFs) will be stored by participant code and no identifying information will be included with CRFs. Study records and data will be kept in a secure location as described below or on restricted-access, password-protected servers. Identifiable information will not be stored with study data. Only the persons named on the Madigan and VA Puget Sound IRB applications will have access to the source documents and original research data. Data will not be revealed to insurance companies or other individuals or organizations.

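### Five exit rules end study participation with no later outcome collection provided for, which conflicts with the ITT analysis and dropout retrieval that section 11.1 relies on

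*Combined protocol and SAP*

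**What the plan says.** Section 13.6 first speaks of stopping treatment: "Participants may be discontinued prematurely from study treatment to manage deterioration of clinical status". The next sentence moves to the study itself: dangerousness, or "emergence of acute psychiatric symptoms necessitating hospitalization will result in discontinuation from the study". A further sentence discontinues from the study anyone whose psychiatric symptoms become markedly worse with severe distress or immediate danger.

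The same pattern appears elsewhere:

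- Section 13.1: "If a participant becomes incarcerated for longer than one day after the Baseline, the participant will be discontinued from the study".
- Section 14.2, on the war zone trauma population: "Participants will be discontinued from the study to manage marked deterioration of clinical status".
- Section 14.2, on women of childbearing potential: "Any woman who becomes pregnant during the course of the study will be discontinued from the study".

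Outcome assessment at exit is spelled out for one route only. A participant who cannot tolerate the minimum dose has this rule in 13.6: "he or she will undergo early termination and all week 13 assessments will be performed". The week 19 paragraph of 10.1 mentions a certificate given then or "at the early discontinuation visit as appropriate", without saying what that visit contains. Section 14.6 refers to a termination visit at which the blind is broken, and lists no outcomes for it either.

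On the analysis side, 11.1 says: "Analysis of the primary outcomes will follow the ITT principal". It expects retrieval of dropouts to leave few missing observations. The GEE uses all observed points. The ANCOVA uses LOCF or the Dawson method. The main week 13 regression has no missing-data rule.

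**The concern.** An ITT comparison at week 13 needs week 13 outcomes from people who have stopped drug. Here, five kinds of event are written as the end of study participation, and nothing provides for measuring those people afterwards.

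Most of these events are unlikely to be independent of drinking on the protocol's own account. Section 9.7 says AUD lowers the threshold for dangerous behaviour and reports a senior soldier's view that trouble usually involves alcohol. Section 9.3 links PTSD severity to AUD severity, and alcohol use to aggression. Dangerousness, psychiatric admission, marked worsening and incarceration may therefore select heavier drinkers.

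If more worsening placebo participants are lost, a true benefit is understated. If the excess is on prazosin, the benefit is overstated or a harm is partly hidden.

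**Working it through.** **1. The plan's own figures.** Section 11.2: 120 / (1 - 0.40) = 200 randomised, as stated. Drinks (30.3, SD 32, against 62, SD 58): pooled SD = sqrt((32² + 58²)/2) = 46.8 and d = 31.7/46.8 = 0.677. With 60 per arm, two-sided 0.05, power is 96.0% (96.5% with the df-weighted SD), against 97% stated. PACS (-2.6, SD 5.8, against -0.3, SD 3.3): pooled SD = sqrt((5.8² + 3.3²)/2) = 4.72, d = 2.3/4.72 = 0.487, power 76.1%, against 76% stated. The arithmetic stands. The point concerns follow-up.

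**2. What is collected after each exit route.**

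| Exit reason | Section | Ends | Outcomes stated at or after exit |
|---|---|---|---|
| Minimum dose not tolerated | 13.6 | early termination | week 13 battery |
| Dangerousness; psychiatric hospitalisation | 13.6, 14.2 | the study | none |
| Marked worsening | 13.6, 14.2 | the study | none |
| Incarceration over one day | 13.1 | the study | none |
| Pregnancy | 14.2 | the study | none |

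The telephone and mail steps in 11.1 are for study visits that cannot be made in person, and are not extended to people who have been discontinued. PACS is taken at baseline and weeks 8, 13 and 19 (10.2). Someone removed before week 8 may therefore have no PACS after baseline. The calendar, taken at every visit, runs up to removal.

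**3. General form of the bias.** Let r be the share removed in an arm, and k how much worse (in SD) removed participants are than retained ones. The full-arm mean is the retained mean + r·k. With the same k in both arms, the retained placebo-minus-prazosin contrast equals the full contrast - k(r_C - r_P). For PACS, assume k = 0.5 to 1.5 and a rate difference of 3 to 10 points:

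- smallest: 0.5 × 0.03 = 0.015 SD, or 0.015/0.487 = 3% of the planned effect;
- largest: 1.5 × 0.10 = 0.15 SD, or 31%;
- equal rates and equal k: zero.

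**4. Illustration on drinks.** Assumptions: log-normal drinks with the 11.2 means and SDs; removal chance 3% at or below 60 drinks a month and h above; removed participants contribute nothing.

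With σ² = ln(1 + (SD/mean)²) and μ = ln(mean) - σ²/2:

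- prazosin: μ = 3.037, σ = 0.866, share above 60 = 11.1%;
- placebo: μ = 3.813, σ = 0.793, share above 60 = 36.1%.

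The part of the mean contributed by values above 60 is mean × Φ((μ + σ² - ln 60)/σ): 10.93 on prazosin and 41.49 on placebo. With p the share above 60, r = 0.03(1 - p) + h·p. The retained mean is [0.97 × (mean - upper part) + (1 - h) × upper part] / (1 - r). At h = 0.50:

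- prazosin: (0.97 × 19.37 + 0.5 × 10.93)/(1 - 0.082) = 26.4;
- placebo: (0.97 × 20.51 + 0.5 × 41.49)/(1 - 0.200) = 50.8;
- difference 24.4, against 31.7 with nobody removed.

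| h | Removed, prazosin | Removed, placebo | Difference | Raw shrinkage | Standardised | Shrinkage |
|---|---|---|---|---|---|---|
| 5% | 3.2% | 3.7% | 31.5 | 0.8% | 0.675 | 0.3% |
| 10% | 3.8% | 5.5% | 30.8 | 2.7% | 0.671 | 0.9% |
| 20% | 4.9% | 9.1% | 29.5 | 7.0% | 0.661 | 2.4% |
| 35% | 6.5% | 14.6% | 27.1 | 14.4% | 0.644 | 4.9% |
| 50% | 8.2% | 20.0% | 24.4 | 23.1% | 0.624 | 7.8% |

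The standardised effect moves less because removing the upper tail also lowers the SD.

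**The case against.** The best defence is that the text is loose rather than restrictive. Nothing bars collection. 13.6 uses treatment and study almost interchangeably, 11.1 anticipates retrieval, 10.1 and 14.6 mention exit visits, and records stay open for 30 days after early discontinuation. A reader might infer that the protocol forbids these outcomes or deletes them from the ITT set. The documents do not support that: they fail to provide for later collection, and data gathered before removal remain usable. That part of the defence stands. It does not supply a retrieval procedure.

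Two other stronger readings also fail. The hospitalisation rule covers acute psychiatric symptoms, not every admission. Pregnancy is not shown to be related to drinking outcome, and about 10% of participants are expected to be women. It shares the wording defect but is not evidence of bias.

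The upper end of the illustration is also open to attack. Sixty drinks a month is about 14 a week (60/30 × 7), below the more-than-21 a week in one arm of inclusion criterion 2 for men. A 20-50% removal chance above that level is therefore severe, and at 5-10% the raw shrinkage is only about 1-3%. In addition, the GEE keeps week 8 values for later removals. LOCF and the Dawson method are planned too, although LOCF would carry forward a value from before the deterioration.

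Finally, these exits may be a small part of the roughly 40% dropout assumed in 11.2. That figure is itself hard to square with few missing observations. No document says how much of it these triggers cause.

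**Conclusion.** The concern holds as a contradiction within the documents. Sections 13.1, 13.6 and 14.2 end study participation without providing for outcomes, while 11.1 relies on ITT and on retrieval that no procedure delivers. Followed as written, this can lose week 13 outcomes after events plausibly tied to drinking, and the week 13 regression has no rule for the gap.

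The size cannot be fixed from the documents. Under the assumed removal chances the raw difference in drinks shrinks by about 1-23% and the standardised effect by about 0-8%. The PACS contrast could move by 0 to 0.15 SD under separate assumptions. The drinks figures assume log-normal data, the pilot effect, removal driven by drinking alone, and nothing kept from removed participants. A reader might take the upper figures as an estimate of bias. They are not one, and the bias may be nil. The change is worth making because it is cheap and restores the comparison the plan promises.

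**What to change.** Leave every clinical stopping rule as it is, and reconcile the wording around it.

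- In 13.1, 13.6 and 14.2, distinguish stopping study drug from withdrawing from follow-up, and state for each exit reason which outcomes are still collected.
- Unless consent is withdrawn, do the outcome assessments at the termination visit, before the blind is broken where possible.
- Still collect the alcohol calendar and PACS at weeks 8 and 13, extending the telephone and mail route in 11.1 to these participants. The calendar is already retrospective, so a late call can cover a gap. For incarceration, collect only after release and with the agreement of the IRBs.
- Include these values in the ITT analysis. Flag any obtained after unblinding or open-label prazosin, because both measures are self-reported and blinded raters do not protect them. Add a sensitivity analysis without the flagged values.
- In 11.1, describe the retrieval procedure, give the week 13 regression a missing-data rule, and add a missing-not-at-random analysis for it.

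The cost is amendment wording and a few calls per removed participant. Some will remain unreachable, and some self-reports will come from people who know their assignment.

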14.0 Risks and Benefits

14.1

Risks of Harm:

Identify all research-related risks of harm to which the subject will be exposed for each research procedure or intervention as a result of participation in this study. Consider the risks of breach of confidentiality, psychological, legal, social, and economic risks as well as physical risks. Do not describe risks from standard care procedures; only describe risks from procedures done for research purposes

Risks of study drug: There are no known absolute contraindications to prazosin. In clinical trials of prazosin, the most frequent adverse reactions were: dizziness (10%), drowsiness (8%), headache (8%), lack of energy (7%), weakness (7%), palpitations (7%), and, nausea (5%). Less frequent adverse reactions (1-4%) reported in clinical trials were: vomiting, diarrhea, constipation, edema, orthostatic hypotension, dyspnea, syncope, vertigo, depression, nervousness, rash, urinary frequency, blurred vision, reddened sclera, epistaxis, dry mouth, and nasal congestion. Fewer than 1% of patients have reported the following (causal relations sometimes not established): abdominal discomfort or pain, liver function abnormalities, pancreatitis, tachycardia, paresthesias, hallucinations, pruritus, alopecia, lichen planus, incontinence, impotence, priapism, tinnitus, diaphoresis, fever, positive ANA titre, and arthralgia.

Rare but serious side effects (less than 1% of people who take prazosin)

- A potentially dangerous side effect of prazosin is priapism (a painful erection of the penis in men and a similar condition in women that lasts for hours). Participants will be instructed to seek medical attention if this side effect is experienced and if it lasts longer than 4 hours.
Less likely side effects (less than 4% of people who take prazosin):
- problems with the digestive system (such as vomiting, diarrhea, constipation, and indigestion)
- drop in blood pressure when standing up, fainting
- vertigo (loss of balance)
- shortness of breath
- depression
- nervousness
- rash
- edema
- increased urinary frequency
- blurred vision and reddened eyes
- dry mouth
- nasal congestion and nose bleeds

Likely side effects (less than 10% of people who take prazosin)

- nausea (4.9%)
- palpitations or abnormal heart beat (5.3%)
- weakness (6.5%)
- lack of energy (6.9%)
- drowsiness (7.6%)
- headache (7.8%)

More likely side effects

- dizziness and/or lightheadedness (10.3%)

Prazosin may cause syncope. In most cases this is believed to be due to excessive postural hypotension although occasionally the syncopal episode has been preceded by severe tachycardia with heart rates of 120-180 beats per minute. Syncopal episodes have usually occurred within 30-90 minutes of the initial dose. The incidence of the syncopal episodes is 1% if the initial dose is 2 mg or more. Clinical trials suggest that syncopal episodes can be minimized by starting with a dose of 1 mg and slowly titrating up to the final dose, as we are doing in this study.

In post-marketing experience, Intraoperative Floppy Iris Syndrome (IFIS) has been observed during cataract surgery in some patients who are taking or have taken alpha-1 blockers. The patient's ophthalmologist should be prepared for possible modifications to the surgical technique to reduce the surgical risk of IFIS. If a patient needs to have cataract surgery, he/she should tell his/her eye surgeon that he/she may have taken prazosin in a research study.

Prazosin should not be taken concurrently with trazodone. Potential participants who are taking trazodone for sleep and who are willing to discontinue will be washed out before starting this study. Care should be taken when alpha-1 blockers are combined with erectile dysfunction medications. We will be following VA pharmacy prescribing guidelines regarding these medications. Erectile dysfunction medications will not be allowed during the titration period. Once stable dose has been reached, participants will be allowed to use ED drugs at half the usual clinical dose.

Participants will be monitored at each visit for adverse events. Any adverse event will be managed by the study team as clinically appropriate. If necessary, a participant will be referred for treatment of an adverse event. Adverse event reporting will begin after the dispensing of the first dose of study drug. All events reported prior to dispensing of the first dose of study drug shall be part of the participant's health history.

Risks of Questionnaires and Assessments: The interviews and questionnaires may cause participants to focus their attention on traumatic experiences and as a result may produce transient subjective distress or to increase the symptoms of PTSD. There are also sensitive and potentially embarrassing questions regarding alcohol use and whether the participant has had any DUIs. Our study team has experience in conducting interviews and administering these questionnaires to persons with and without PTSD.

Risks of Loss of Confidentiality: There is a risk of loss of confidentiality. We will take all due care so that responses to questionnaires are not commingled with patient medical records. Source documents (which may contain identifying information) will be maintained in locked cabinets within a locked office. Source documents and case report forms will be stored separately. The paper documents will be stored in compliance with record storage policies at VA Puget Sound. Electronic records are in restricted-access folders (only the study team is able to access the folders) on the VA Puget Sound server.

Risks of blood draw: Having blood drawn might cause some discomfort. Removal of blood by a needle and syringe may cause pain or bruising at the site of the needle stick. There is also a slight risk of infection where we insert the needle. Some people may become dizzy or faint when they get their blood drawn.

14.2

Measures to Minimize Risks of Harm (Precautions, safeguards):

For each research procedure or intervention, describe all measures to minimize and/or eliminate risk of harms to subjects and study personnel

Protection against adverse effects of prazosin: Participants will undergo screening evaluation including review of medical and psychiatric history, physical examination and 12-lead ECG (if clinically indicated). Seated/supine and standing BP and HR will be monitored at each in-person study visit.

Women of childbearing potential must have a negative urine pregnancy test at screen and within one week of starting study drug. Female participants must agree to abstain from sexual relations that could result in pregnancy or use an effective method of birth control acceptable to both participant and the study clinician during the study in order to be eligible. Women who are nursing will not be eligible for study participation. Any woman who becomes pregnant during the course of the study will be discontinued from the study but will continue with customary AUD treatment or treatment with her DBH provider.

Risks of medication side effects will be minimized by starting at a low dose and titrating up to the maximum dose over a period of weeks, by maintaining frequent contact with study participants, and by performing safety assessments on a regular schedule. As a further precaution, male participants will be advised to sit on the toilet for urination during the first week of dose titration.

Vital signs, including orthostatic BP and HR, will be performed at all in-person study visits. Systolic and diastolic BP and HR will be obtained following at least 10 minutes of seated/supine posture and then repeated following 2 minutes of standing. Occurrence of lightheadedness, dizziness on standing, palpitations, drowsiness, headache, nausea, nasal congestion, peripheral edema, and other adverse effects will be rated by a study clinician. For vital signs parameters, unacceptable side effects will include seated/supine hypotension (seated/supine systolic BP < 90) and clinically meaningful orthostatic hypotension (≥ 20 mmHg drop in systolic BP accompanied by lightheadedness or syncope).

Safety procedures specific to the war zone trauma population: Participants will be discontinued from the study to manage marked deterioration of clinical status or if the study clinician determines the participant is not stable enough to continue participation. For example, psychiatric symptoms become markedly increased resulting in severe participant distress, dangerousness toward self or others or emergence of acute psychiatric symptoms necessitating hospitalization. Study termination will be followed by a warm hand-off to DBH personnel. DBH personnel will assume responsibility for arranging appropriate care. A study clinician will be on call at all times to receive telephone calls from participants regarding any adverse events; participants will be provided with a 24-hour emergency contact number.

Participants are asked about suicidal ideation at each visit. If endorsed, participants will be assessed as to their level of risk and the level of care required to keep themselves or others from harm. If a participant requires inpatient treatment in order to prevent harm or is found to have symptoms of disorganized thought processes secondary to psychosis, DBH personnel will be notified immediately to assist with appropriate triage and referral.

Protection against risk of loss of confidentiality: Confidentiality is strict. All case report forms (CRFs) will be stored by participant code and no identifying information will be included with CRFs. Study records and data will be kept in a secure location as described below or on restricted-access, password-protected servers. Identifiable information will not be stored with study data. Only the persons named on the Madigan and VA Puget Sound IRB applications will have access to the source documents and original research data. Data will not be revealed to insurance companies or other individuals or organizations.

Exceptions to confidentiality: The study team will have access to participant medical records from initial consent until 30 days beyond the end of participant study participation to monitor for adverse events and treatment progress. Participant endorsement of illegal substance use, and any self-harm, suicidal or homicidal disclosures will be shared with DBH personnel. Results of the screening labs and GGT testing will be placed in the participants' AHLTA record and will be available to any of the participant's other Army health care providers or any health care providers to whom a participant releases his/her medical records.

14.3

Confidentiality Protections (for research records, data and/or specimens):

Describe in detail the plan to maintain confidentiality of the research data, specimens, and records throughout the study and at its conclusion (e.g., destruction, long term storage, or banking). Explain the plan for securing the data (e.g., use of passwords, encryption, secure servers, firewalls, and other appropriate methods). If data will be shared electronically with other team members/collaborators outside the institution, describe the method of transmission and safeguards to maintain confidentiality. Explain whether this study may collect information that State or Federal law requires to be reported to other officials or ethically requires action, e.g., child or spouse abuse

All study information will be recorded on standardized case report forms (CRFs). CRFs will be labeled with study code number only. Code numbers will be assigned sequentially and will not include participant initials or any other identifiers.

Data will be stored on a secure VA server with restricted access. Only the persons named on the Madigan and VA Puget Sound IRB applications will have access to the source documents and original research data. Data will not be revealed to insurance companies or other individuals or organizations. The code list will be stored on a VA Puget Sound server in a restricted-access folder, which is only accessible by persons named on the protocol. The VA Puget Sound server complies with current Federal standards.

Identifying information will be kept in the participants' paper study source document file. The research files will be transported the same day from JBLM, a Joint Commission compliant records storage facility, to the VA Puget Sound Seattle, a Joint Commission compliant records storage facility. The research files will be transported in HIPAA compliant secured containers by selected members of the study staff and will only be accessible by IRB approved study staff. No research records will be left unattended or unsecured overnight off-site of either JBLM or VA Puget Sound Seattle medical treatment facilities. The research charts and case report forms must be stored at VA Puget Sound because most of the study personnel are located there and must be able to contact participants when necessary to schedule appointments and in case a participant reports an adverse event. Participants are instructed to call VA Puget Sound staff in these cases. Providers for this study are located in offices at JBLM and VA Puget Sound. If at any time information contained in a participant's research chart is required, it can be faxed to the PI. As the study providers are located at multiple locations, the study team will meet on a weekly basis to discuss study participants and any study concerns. This will help the PI to be continually informed regarding all current participants. The files should be most accessible to those who are most likely to respond to the participant needs.

The lead study coordinator, site investigator and overall PI are all responsible for ensuring the continued security of the research records.

14.4

Potential Benefits:

Describe any real and potential benefits of the research to the subject and any potential benefits to a specific community or society

If the individuals in the research are considered experimental subjects (per 10 USC 980), and they cannot provide their own consent, the protocol must describe the intent to directly benefit all subjects

Through participation in this research, all participants will receive additional monitoring and visits in addition to their customary treatment for AUD. Participants will get thorough medical and psychiatric assessments, which may benefit them by providing them information about these assessments. It is possible that participants in the prazosin group will experience additional benefit resulting in reduced alcohol use and decreased PTSD symptoms. Society at large will benefit if improved treatments for AUD are discovered through this research.

14.5

Privacy for Subjects:

Describe the measures to protect subject's privacy during recruitment, the consent process, and all research activities, etc.

SMs engaged in DBH treatment programs who have reported alcohol issues will be asked if they are willing to speak to a research team member about potential participation in the study. If the individual agrees, the staff member will make the referral by contacting the research team. Study personnel will give a brief overview of the study and ask whether the individual is still interested. For individuals who want to learn more, and who meet basic prescreening inclusion criteria, an appointment will be scheduled with a trained investigator who will explain the study in detail and obtain written informed consent as described below. Potential participants who self-refer to the study will be given information about the study and DBH alcohol treatment options.

The study will be explained to eligible participants by one of the approved study personnel in a private setting. DBH personnel will not conduct the initial consent visit.

Although SMs may have command requirements to complete the clinical outpatient JBLM assignment to the SUDCC programs, command pressure to participate in this research study will be strictly avoided.

All study visits occur in private clinic spaces.

14.6

Incidental or Unexpected Findings:

Describe the plan to address incidental findings and unexpected findings about individuals from screening to the end of the subject's participation in the research. In cases where the subject could possibly benefit medically or otherwise from the information, state whether or not the results of screening, research participation, research tests, etc., will be shared with subjects or their primary care provider. State whether the researcher is obligated or mandated to report results to appropriate military or civilian authorities and explain the potential impact on the subject

It is possible that participants in the prazosin group will experience additional benefit resulting in reduced alcohol use and decreased PTSD symptoms.

Participants will be monitored at each visit for adverse events. Any adverse event will be managed by the study team as clinically appropriate. If necessary, a participant will be referred for treatment of an adverse event.

At the study termination or the week 13 visit, all participants will be offered a follow-up appointment with a DBH provider or clinical health care providers. The blind will be broken at participant termination visit regardless of participant trial completion. (All raters will remain blind and will not be informed of any instances of breaking the blind).

We recognize that not breaking the blind for each participant until all participants have completed the protocol is ideal. However, the appropriate and safe method of initiating open-label prazosin by necessity differs depending on the study drug received in the double-blind study (prazosin or placebo).

